10. APPENDICES

10.1 MAYO SCORE

The Mayo score (R16-4416) is a composite disease activity score consisting of four items or subscores: stool frequency (relative to normal), rectal bleeding, physician's global assessment, and endoscopic appearance. As proposed by FDA draft guidance (R17-0038), the endoscopic subscore is modified so that a value of 1 does not include friability. The overall range of the Mayo score is 0-12 (higher scores being worse) and each subscore has a range of 0-3 (Table 10.1: 1). At visits without sigmoidoscopy, a partial Mayo score without endoscopy subscore will be assessed. The overall range of this partial Mayo score is 0-9.

In addition, based on FDA's recommendation ($\underline{R17-0038}$), a modified Mayo score will be assessed, which excludes physician's assessment. The overall range of the modified Mayo score is 0-9.

The scores for stool frequency and rectal bleeding will be calculated as an average of the last 3 non-missing entries (from the patient daily diary) within the week prior to each applicable visit. If the patient undergoes bowel preparation for endoscopy on any of the days before a visit, the stool frequency and RBS for that day(s) should be considered missing. In addition, the stool frequency and RBS will be considered missing for the day of and the day after all endoscopies.

The endoscopic appearance score will be assessed by a central reader, who is independent from the investigator.

Boehringer Ingelheim BI Trial No.: 1368-0004 c10710598-04

Subscore

(daily)

Stool Frequency^a

Trial Protocol

03 Apr 2019

Proprietary confidential information © 2019 Boehringer Ingelheim International GmbH or one or more of its affiliated companies

Score

0

1

2

3

3

Table 10.1: 1Mayo score (adapted from Schroeder et al, 1987 (R16-4416))

Normal number of stools for patient

1 to 2 stools more than normal

3 to 4 stools more than normal

 \geq 5 stools more than normal

Severity

		•
Rectal Bleeding ^b (daily)	No blood seen	0
	Streaks of blood with stool	1
	Obvious blood with stool	2
	Blood alone passes	3
Physician's Global Assessment ^c	Normal	0
	Mild disease	1
	Moderate disease	2
	Severe disease	3
	Normal	0
Endoscopic Appearance ^d	Mild disease	1
	Moderate disease	2

^a Each patient serves as his or her own control to establish the degree of abnormality of the stool frequency.

^b The daily bleeding score represents the most severe bleeding of the day.

Severe disease

^c The physician's assessment acknowledged the three other criteria, the patient's daily record of abdominal discomfort and general sense of well-being, and other observations, such as physical findings and the patient's performance status.

^d Modified endoscopic appearance: 0 (normal), Mild (erythema, decreased vascular pattern), Moderate (marked erythema, loss of vascular pattern, any friability, erosions), Severe (spontaneous bleeding, ulceration).

Page 75 of 82

Proprietary confidential information © 2019 Boehringer Ingelheim International GmbH or one or more of its affiliated companies

Page 76 of 82

Proprietary confidential information © 2019 Boehringer Ingelheim International GmbH or one or more of its affiliated companies

11. DESCRIPTION OF GLOBAL AMENDMENT(S)

Number of global amendment	1	
Date of CTP revision	16 Jan 2018	
EudraCT number	2017-000100-20	
BI Trial number	1368-0004	
BI Investigational Product(s)	BI 655130	
Title of protocol	Exploratory Trial to Assess Mechanism of Action, Clinical Effect, Safety and Tolerability of 12 Weeks of Treatment with BI 655130 in Patients with Active Ulcerative Colitis (UC)	
To be implemented only after approval of the IRB / IEC / Competent Authorities	X	
To be implemented immediately		
in order to eliminate hazard –		
IRB / IEC / Competent Authority to be notified of		
change with request for		
approval		
Can be implemented without IRB / IEC / Competent		
Authority approval as changes		
involve logistical or administrative aspects only		
auministrative aspects only		
Section to be changed	Across whole protocol	
Description of change	Trial number 1368.4 was changed to 1368-0004	
Rationale for change	To implement new format of trial number across trial documents for consistency reason	
Section to be changed	CLINICAL TRIAL PROTOCOL SYNOPSIS	
Description of change	The lower body weight limit of 60 kg was deleted.	
Rationale for change	A lower body weight limit is not needed any more.	
Section to be changed	FLOW CHART	
Description of change	For some visits, total Mayo Score (" ^T ") was replaced by partial Mayo Score (" ^P ").	
Rationale for change	To correct a typographical error.	
Section to be changed	FLOW CHART	
Description of change	Sigmoidoscopy at 4 hours after the first i.v. infusion was deleted. All biopsy samples should be obtained prior to IMP administration.	

0710598-04Trial ProtocolPage 77 of 82Proprietary confidential information © 2019 Boehringer Ingelheim International GmbH or one or more of its affiliated companies

Rationale for change	To reduce the overall number of sigmoidoscopies in this trial.	
Section to be changed	FLOW CHART	
Description of change	The time-point of EoO visit was corrected.	
Rationale for change	To ensure that EoO visit will take place after the end of the residual effect period of the IMP.	
Section to be changed	FLOW CHART	
Description of change	It was added that patients who completed regular treatment in trial 1368-0004 would be offered to enter the long-term extension trial 1368-0017.	
Rationale for change	To add option for long-term treatment for patients who completed regular treatment.	
Section to be changed	1.2 DRUG PROFILE	
Description of change	Information from study 1368.1 and 1368.2 and from population pharmacokinetic modelling was updated.	
Rationale for change	To update safety information on BI 655130 and provide rationale why the lower body weight limit is not needed anymore.	
Section to be changed	2.3 BENEFIT-RISK ASSESSMENT	
Description of change	Information from study 1368.1 and 1368.2 and from population pharmacokinetic modelling was updated.	
Rationale for change	To update safety information on BI 655130 and provide rationale why the lower body weight limit is not needed anymore.	
Section to be changed	2.3 BENEFIT-RISK ASSESSMENT	
Description of change	It was added that patients who completed 12 weeks treatment duration would be offered long-term treatment in trial 1368-0017.	
Rationale for change	To include the option for long-term treatment for patients who completed regular treatment in the risk-benefit assessment, as long-term treatment for these patients is considered an individual benefit.	
Section to be changed	3.1 OVERALL TRIAL DESIGN AND PLAN	
Description of change	It was added that patients who complete regular treatment can receive long-term treatment in trial 1368-0017.	
Rationale for change	To update the trial design regarding the option for long-term treatment for patients who complete regular treatment in trial 1368-0004.	
Section to be changed	3.3.1 Main diagnosis for trial entry	
Description of change	The trial population was extended to patients who were treated with TNF antagonist(s) previously but did not stop that treatment due to primary non-	

0710598-04Trial ProtocolPage 78 of 82Proprietary confidential information © 2019 Boehringer Ingelheim International GmbH or one or more of its affiliated companies

	1 6	
	response or loss of response	
Rationale for change	To update trial population with the aim to facilitate recruitment	
Section to be changed	3.3.2 Inclusion criteria	
Description of change	The lower body weight limit of 60 kg was deleted.	
Rationale for change	A lower body weight limit is not needed any more.	
Section to be changed	3.3.2 Inclusion criteria	
Description of change	The trial population was extended to patients who were treated with TNF antagonist(s) previously but who stopped treatment for other reasons than primary non- response or lack of response. The reason for stopping treatment has to be documented in the source data.	
Rationale of change	To update trial population with the aim to facilitate recruitment.	
Section to be changed	3.3.3 Exclusion criteria	
Description of change	The trial population was extended to patients who were treated with TNF antagonist(s) previously but did not stop that treatment due to primary non- response or loss of response	
Rationale for change	To update trial population with the aim to facilitate recruitment.	
Section to be changed	3.3.3.3 General exclusion criteria	
Description of change	Unit for haemoglobin was corrected to g/dL.	
Rationale for change	To correct error.	
Section to be changed	3.3.3 Exclusion criteria	
Description of change	The numbering of exclusion criteria was changed so that it is continuous.	
Rationale for change	To update numbering of exclusion criteria so that it is consistent with the numbering in the BRAVE system.	
Section to be changed	4.1.2 Selection of doses in this trial	
Description of change	The lower body weight limit of 60kg was deleted.	
Rationale for change	A lower body weight limit is not needed anymore.	
Section to be changed	Section 4.2.1 Other treatments and emergency procedures	
Description of change	Further guidance has been added regarding infusion reactions, cytokine release syndrome and infections.	
Rationale for change	To provide guidance to the investigator for infusion reactions, cytokine release syndrome and infections.	
Section to be changed	Section 4.2.2 Restrictions	

Page 79 of 82

Proprietary confidential information © 2019 Boehringer Ingelheim International GmbH or one or more of its affiliated companies

Description of change	The information regarding biologics treatment was updated to allow previous TNF antagonist(s) treatment, if stopped for other reasons than primary non- response or lack of response. Also, it was added, that the last dose of TNF antagonist(s) treatment has to be at least 8 weeks or 3 half-lives, whichever is longer, from screening.	
Rationale for change	To update restrictions regarding the previous use of biologics.	
Section to be changed	Section 5.3.5.1 Definitions of adverse events	
Description of change	Infusion reactions including anaphylactic reactions, cytokine release syndrome and opportunistic and mycobacterium tuberculosis infections were added to adverse events of special interest (AESIs).	
Rationale for change	To update section on AESIs so that it is consistent across the BI 655130 project.	
Section to be changed	Section 6.2.1 Screening and run-in period	
Description of change	The information regarding the patient diary was changed, as daily reporting of CMs is not included in the current diaries, but the patients have to confirm regular intake of CMs before each visit.	
Rationale for change	To change description of the diaries to clarify that daily reporting of CM intake is not included.	
Section to be changed	6.2.3 Follow up period and Trial Completion	
Description of change	It was added that patients who complete regular treatment can receive long-term treatment in trial 1368-0017. EoO visit would be on the same day as EoT visit.	
Rationale for change	To clarify the time-point of trial completion for patients who enter long-term extension trial 1368- 0017.	
Section to be changed	Section 7.3 PLANNED ANALYSES	
Description of change	It was clarified that the set for the primary evaluation of gene expression includes all patients who completed trial medication and trial throughout EOT visit and who provide at least one evaluable baseline and one evaluable post-baseline biopsy RNA measurement.	
Rationale for change	To clarify description of the patient set for the primary evaluation of gene expression.	
Section to be changed	Section 7.3.1 Primary endpoint analyses	
Description of change	"log2" was removed.	
Rationale for change	To correct an error.	
Section to be changed		

Page 80 of 82

Proprietary confidential information © 2019 Boehringer Ingelheim International GmbH or one or more of its affiliated companies

Description of change		
Rationale for change		
Section to be changed	Section 9.1 PUBLISHED REFERENCES	
Description of change	To add two additional references.	
Rationale for change	To update Section 9.1 regarding two additional references.	
Section to be changed	Section 10.2 MAYO SCORE	
Description of change	In Table 10.2: 1, "granularity" was deleted from footnote d.	
Rationale for change	To correct assessment of modified endoscopic response, according to established criteria for Mayo Score.	
Section to be changed	Section 10.3 EQUIVALENT DOSES OF CORTICOSTEROIDS	
Description of change	"16-Methylprednisolone" was deleted from the table.	
Rationale for change	To correct typographical error.	
Section to be changed	10.3 EQUIVALENT DOSES OF CORTICOSTEROIDS	
Description of change	To add equivalent doses of budenoside.	
Rationale for change	To update table with information for budesonide.	

Number of global amendment	2
Date of CTP revision	18 May 2018
EudraCT number	2017-000100-20
BI Trial number	1368-0004
BI Investigational Product(s)	BI 655130
Title of protocol	Exploratory Trial to Assess Mechanism of Action, Clinical Effect, Safety and Tolerability of 12 Weeks of Treatment with BI 655130 in Patients with Active Ulcerative Colitis (UC)
To be implemented only after approval of the IRB / IEC / Competent Authorities	X
To be implemented immediately in order to eliminate hazard –	

0710598-04Trial ProtocolPage 81 of 82Proprietary confidential information © 2019 Boehringer Ingelheim International GmbH or one or more of its affiliated companies

IRB / IEC / CompetentAuthority to be notified ofchange with request forapprovalCan be implemented withoutIRB / IEC / CompetentAuthority approval as changesinvolve logistical oradministrative aspects only			
	L		
Section to be changed	FLOW CHART		
Description of change	The time-point of FU1 visit was corrected.		
Rationale for change	To correct an error.		
Section to be changed	FLOW CHART		
Description of change	Sigmoidoscopy with biopsy sample collection and blood sampling for gene expression and methylation pattern analysis at 4 hours after the first i.v. infusion was re-included.		
Rationale for change	Based on expert PI feedback.		
Section to be changed	Section 3.3.3		
Description of change	The numbering of the exclusion criteria was corrected.		
Rational for change	To correct an error.		
Section to be changed	Section 6.2.2		
Description of change	It was clarified that an additional sigmoidoscopy will take place at 4 hours after first i.v. infusion to collect biopsy samples. Also, it was clarified that an additional blood sample will be collected at 4 hours after first i.v. infusion for gene expression and methylation pattern analysis.		
Rationale for change	Based on expert PI feedback.		
Section to be changed	Section 7.3.1		
Description of change	A typographical error was corrected.		
Rationale for change	To correct an error.		
Section to be changed	Section 7.6		
Description of change	The description of the number ranges per site was updated.		
Rationale for change	Additional study sites are planned to be included.		
Section to be changed	Section 11		
Description of change	The word "biologics" was replaced by "TNF antagonist(s)" in the description of changes related to sections 3.3.1, 3.3.2, 3.3.3 and 4.2.2.		

Boehringer Ingelheim BI Trial No.: 1368-0004

Trial Protocol

Page 82 of 82

03 Apr 2019

[figure not shown]

2. LIST OF ABBREVIATIONS

Term	Definition / description
ADA	Anti-drug antibodies
ADS	Analysis dataset
AE	Adverse event
AESI	Adverse event of special interest
ALT	Alanine aminotransferase
AP	Alkaline phosphatase
5-ASA	5-Aminosalicylate
AST	Aspartate aminotransferase
ATC3	Anatomical-Therapeutic-Chemical classification level 3
BI	Boehringer Ingelheim
BLQ	Below the lower limit of quantification
BMI	Body mass index
CARE	Clinical data analysis and reporting environment
C _{max}	Maximum measured concentration of the analyte in plasma
CRF	Case report form
CRP	C-reactive protein
CTP	Clinical trial protocol
CTR	Clinical trial report
CV	Arithmetic coefficient of variation
DBLM	Database lock meeting
DILI	Drug Induced Liver Injury
DMC	Data Monitoring Committee
DNA	Deoxyribonucleic acid
ECG	Electrocardiogram
eCRF	Electronic case report form
EMA	European Medicines Agency
ELISA	Enzyme Linked Immunosorbent Assay
EoO	End of Observation
ЕоТ	End of trial
ES	Enrolled set
EudraCT	European union drug regulating authorities clinical trials

Term	Definition / description
FACIT	Functional Assessment of Chronic Illness Therapy
FAS	Full analysis set
F/U	Follow-up
gCV	Geometric coefficient of variation
gMean	Geometric mean
ICH	International Council for Harmonisation of Technical Requirements for Pharmaceuticals for Human Use
IL IL-36R IMP iPD	Interleukin Interleukin-36 Receptor Investigational medicinal product important protocol deviation
MedDRA	Medical Dictionary for Regulatory Activities
MQRM	Medical quality review meeting
MTX	Methotrexate
6-MP	6-Mercaptopurine
NOA	Not analysed
NOR	No valid result
NOS	No sample available
OC	Observed cases
OC-IR	Observed cases including values after rescue medication
OR	Original results
PD	Pharmacodynamic(s)
PG	Pharmacogenomic(s)
РК	Pharmacokinetic(s)
PKS	Pharmacokinetic parameter set
PPS	Per protocol set
PT	Preferred Term
Q1	1 st quartile
Q3	3 rd quartile
RAGe	Report appendix generator
RBS	Rectal Bleeding Subscore
REP	Residual effect period

 TSAP for BI Trial No: 1368-0004
 Page 6 of 48

 Proprietary confidential information © 2019 Boehringer Ingelheim International GmbH or one or more of its affiliated companies

Definition / description Term RNA **Ribonucleic Acid** RNAseq **RNA** sequencing RPM Report planning meeting Serious adverse event SAE SD Standard deviation SDL Subject data listing SFS stool SI Système international d'unités **SMQ** Standardised MedDRA query Transforming Growth Factor beta TGF-β TNF Tumour Necrosis Factor TS Treated set TSAP Trial statistical analysis plan Ulcerative Colitis UC ULN Upper limit of normal range

Proprietary confidential information © 2019 Boehringer Ingelheim International GmbH or one or more of its affiliated companies

VEGF	Vascular Endothelial Growth Factor
V L'OF	

Page 7 of 48

3. INTRODUCTION

As per ICH E9 (1), the purpose of this document is to provide a more technical and detailed elaboration of the principal features of the analysis described in the CTP and its amendments, and to include detailed procedures for executing the statistical analysis of the primary and secondary variables and other data.

This TSAP assumes familiarity with the CTP. In particular, the TSAP is based on the planned analysis specification as written in CTP Section 7 "Statistical Methods and Determination of Sample Size". Therefore, TSAP readers may consult the CTP for more background information on the study, e.g., on study objectives, study design and population, treatments, definition of measurements and variables, and planning of sample size.

Study data will be stored in a trial database within BRAVE system.

The statistical analyses will be performed within the validated working environment CARE, including SASTM (current Version 9.4, by SAS Institute Inc., Cary, NC, USA), and a number of SASTM-based tools (e.g., macros for the analyses of AE data or laboratory data; Report Appendix Generator system (RAGe) for compilation/formatting of the CTR appendices).

R version 3.1.2 or later ($\underline{6}$), Bioconductor version 2.13 or later, and the DESeq-package version 3.18.13 or later will be used in the analyses of gene expression data. Genome version hg38/GRCh38 will be used in conjunction with Ensembl version 84 or later.

This TSAP describes the analyses of BMs defined as endpoints and planned to be reported in the CTR.

4. CHANGES IN THE PLANNED ANALYSIS OF THE STUDY

The following changes of endpoints (based on Mayo score) were implemented to be consistent across trials.

The following renamings were conducted:

- The secondary endpoint clinical remission (Mayo Score ≤2 with all subscores ≤1) will be labelled as *total clinical remission*
- The further endpoint Modified clinical remission (Mayo Score ≤2 AND (A) rectal bleeding subscore (RBS) = 0, (B) modified endoscopic subscore ≤1; and (C) stool frequency subscore = 0 or =1 and drop ≥ 1 from baseline) will be labelled as *clinical remission*

See Section 9.1 for details on deriving the efficacy endpoint scores at each visit.

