5.2.2 Secondary endpoints

5.2.2.1 Secondary efficacy endpoints

The following secondary efficacy endpoints will be analysed:

- Percent change in CRP from baseline to Week 12
- *Percent change in faecal calprotectin from baseline to Week 12*
- Percent change in faecal lactoferrin from baseline to Week 12
- Total clinical remission (defined as Total Mayo score ≤2 points, and all subscores ≤1 point) at Week 12 (cf. Section 4)

For details on calculating the total Mayo score at each visit, cf. Section 9.1.

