7.5.2 Secondary endpoints

7.5.2.1 Secondary efficacy endpoints

The analysis of CRP, FCP and FLFwill be performed as defined in Section 7.3.2 of the CTP and will be based on the SAF.

The CRP, FCP and FLF will be descriptively summarized by visit as continuous variables. For each marker the absolute value and percent change from baseline will be analysed per treatment group via

• Mean, standard deviation, median, Q1, Q3, normalized IQR (0.7413*IQR), minimum, maximum, gMean

- Error bars for the median with Q1 being the lower end and Q3 the upper end of the bars of the respective outcome variable will be calculated for each time point. This information will be displayed graphically in conjunction with the median.
- Line plots presenting individual values of the respective outcome variable over time. Beside the individual patient lines also a median line will be depicted in all plots for a better visual interpretation.

In plots with absolute values reference lines indicating LLOQ and ULOQ may be included. In addition lower and upper limit of the normal range, if a normal range is available, will be presented.

The analysis of secondary efficacy endpoints will be performed as defined in Section 7.3.2 of the CTP and will be based on the FAS.

Total clincal remission at Week 12 will be assessed based on the proportion of patients with Total Mayo score ≤ 2 points, and all subscores ≤ 1 point (cf. Section 9.1.1). The proportion of patients with total clinical remission will be summarized descriptively by visit, presenting patient frequencies and proportions together with exact 95% Wilson score confidence intervals.

Additional displays of the patient frequencies and percentages for the individual total Mayo scores (resp. partial MCS), as well as for each of the four subscore (SFS, RBS, PGA and mESS; cf. Section 9.1.1) will also be produced. Furthermore line plots will be produced presenting Mayo score (resp. the Mayo subscores SFS, RBS, PGA and mESS) over time.

 TSAP for BI Trial No: 1368-0004
 Page 35 of 48

 Proprietary confidential information © 2019 Boehringer Ingelheim International GmbH or one or more of its affiliated companies

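### Unless SAP 9.1 rounds the stool frequency subscore, the equality test in the further endpoint 'clinical remission' rejects averages of 0.33 and 0.67 but can accept 1.00

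*SAP*

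**What the plan says.** Protocol 10.1 (Mayo score) sets the scale, "each subscore has a range of 0-3", and the derivation: "The scores for stool frequency and rectal bleeding will be calculated as an average of the last 3 non-missing entries", drawn from the diary in the week before the visit. The protocol gives no rounding step.

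SAP Section 4 renames two remission endpoints. The one introduced as "The further endpoint Modified clinical remission" becomes clinical remission. It needs a Mayo score of at most 2, a rectal bleeding subscore of 0, "modified endoscopic subscore ≤1", and "stool frequency subscore = 0 or =1 and drop ≥ 1 from baseline". The section then points to SAP 9.1 "for details on deriving the efficacy endpoint scores at each visit".

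The secondary endpoint is defined separately in SAP 5.2.2.1: "Total clinical remission (defined as Total Mayo score ≤2 points, and all subscores ≤1 point) at Week 12".

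**The concern.** An average of three daily scores on a 0 to 3 scale need not be a whole number. A test for exact equality to 0 or 1 suits whole-number scores. Applied to an average, it leaves a gap between 0 and 1 in which patients with fewer stools than an accepted patient are turned away. The endoscopic condition in the same definition is an upper limit, which suggests that the equality was written with whole-number scores in mind.

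At stake is the rate reported under the unqualified label clinical remission. If the averages are used as they stand, that rate does not follow disease activity, and a programmer who codes the definition as written would not notice.

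**Working it through.** The plan states no figure to reproduce for this point. The check applies the written condition to every possible three-day average.

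**Inputs**
- Daily stool frequency score 0, 1, 2 or 3; subscore x = (d1 + d2 + d3)/3, no rounding (Protocol 10.1).
- Stool frequency condition, with b the baseline subscore (SAP 4): x = 0, or x = 1 with b − x ≥ 1. The text can also be read as x equal to 0 or 1, with b − x ≥ 1 required in both cases. The two readings differ only when x = 0 and b < 1.

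**Step 1: possible values.** There are 4³ = 64 ordered triples of daily scores. Of these, 42 give a non-integer average. Twenty triples have an average of at most 1: one at 0, three at 0.33, six at 0.67 and ten at 1.00. So 3 + 6 = 9 of the 20 fall on thirds. These counts show which values can occur. They are not patient probabilities.

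**Step 2: the stool frequency condition at a baseline of 2, 2.33 or 3.** Both readings give the same results here.

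| Days | x | As written, unrounded | At most 1 in place of equality | Rounded to nearest integer, then as written |
|---|---|---|---|---|
| 0,0,0 | 0 | pass | pass | pass |
| 0,0,1 | 0.33 | fail | pass | pass |
| 0,1,1 | 0.67 | fail | pass | pass |
| 1,1,1 | 1.00 | pass | pass | pass |
| 1,1,2 | 1.33 | fail | fail | pass |

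**Step 3: a full record.** Take baseline stool frequency 2.33, rectal bleeding 0, endoscopy 1 and physician's assessment 0. The Mayo total is x + 0 + 1 + 0, which is 1.00, 1.33, 1.67 and 2.00 for x = 0, 0.33, 0.67 and 1.00. All are at most 2. The drops from baseline are 2.33, 2.00, 1.67 and 1.33, all at least 1. Nothing but the equality separates the four records, and it rejects the middle two.

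**Step 4: where the inversion stops.** At a baseline of 1, 1.33 or 1.67, x = 1.00 also fails because the drop is below 1, so no worse patient with the same baseline is accepted. The inversion therefore needs a baseline of at least 2. The bleeding condition has no such problem, because an average of 0 means that all three days are 0.

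**Step 5: weight of one patient.** With 10 patients, 1/10 = 10 percentage points.

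**The case against.** The strongest reply is that the derivation belongs to SAP 9.1, to which Section 4 refers directly after the definition. That section is not in the text available here, which is no fault of the plan, and it may round. There are signs that whole numbers are expected: the Mayo table in Protocol 10.1 lists integer categories, and SAP 7.5.2.1 plans frequencies for the "individual total Mayo scores (resp. partial MCS), as well as for each of the four subscore". Neither settles the matter, but the inversion can only be stated conditionally.

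A reader might infer that the plan is wrong either way, because rounding in 9.1 would contradict the protocol. The documents do not support that. Protocol 10.1 is silent on rounding, and the SAP introduction describes the SAP as the place for technical elaboration, so a rounding step there would add detail to the protocol, not conflict with it.

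A reader might also extend the point to total clinical remission or to the eligibility limits (Mayo score at least 6, rectal bleeding at least 1). Those are inequalities and work for fractions. Rounding could change who meets them, but that is a difference between two conventions and not an error in the rule.

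Finally, the proposed wording still does not rank patients with different baselines by final score alone. A change from 1.00 to 0.33 (drop 0.67) fails, while 2.00 to 1.00 passes. That is true, but it follows from the required drop, which is part of the endpoint. For a given baseline, the ordering becomes correct.

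**Conclusion.** The point holds conditionally. On the visible text, an unrounded average is tested by equality, and for a baseline of at least 2 with all other conditions met, 0.33 and 0.67 are non-remission while 1.00 is remission. If SAP 9.1 rounds to whole numbers, there is no inversion.

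The reach is narrow: one descriptive further endpoint. The primary endpoint does not use the Mayo score as an outcome, and the secondary remission endpoint does not contain the equality.

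It may be tempting to say that the remission rate is understated by some stated fraction. The documents do not support a figure. It would need the distribution of daily scores near remission and the correlation between days within a patient, and neither is given. What can be said is that the effect is zero if scores are rounded, and otherwise 10 percentage points for each affected patient among 10.

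**What to change.** In SAP Section 4, and in 9.1 where the endpoint is derived, replace the equality by this condition: the stool frequency subscore is 0, or it is at most 1 and at least 1 below baseline.

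If subscores are rounded, the only values up to 1 are 0 and 1, so the result is the same as under the present wording with the drop attached to the value 1. The new wording also makes that reading explicit. If subscores are not rounded, the inversion disappears. The change does not itself decide on rounding; an average of 1.33 passes only if it is rounded first, so that choice stays with the derivation in 9.1.

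The cost is a wording change and one line of derivation code. No data collection or other endpoint is touched.
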